3.5 Settings and Materials

3.5.1 Settings

The study will be conducted either in the spaces provided by the partner community organizations (e.g. assistive living facilities) or in Room 1-43 or 1-45 of the Corbett Hall, at the Faculty of Rehabilitation Medicine, University of Alberta.

3.5.2 Materials

A 13-inch Dell Latitude 5411 laptop, equipped with an Intel(R) Core (TM) i7-10850H CPU, 16 GB RAM, and a Microsoft mouse, customized for both left and right-handed individuals, will be used to play the game. The game G3, will be utilized for the game-based screening.

G3 was designed to simulate grocery shopping, aiming at challenging cognitive skills in a fun and engaging way. Originally developed in Edmonton, Alberta, by Glenrose Rehabilitation

Research, Innovation & Technology (GRRIT), the game was created in collaboration with occupational therapists to meet the specific needs of older adults. G3 consists of 50 stages and was initially intended for cognitive training. However, in this study, it will be tested for the first time as a cognitive screening tool.

The game features stages with varying difficulty levels (easy, normal, hard), based on the number of items in the shopping list, according to needed ingredients for a meal. For this study, six stages will be selected for participants to play. Players take a virtual trip to the grocery store to shop for ingredients of a virtual dinner for celebrity guests. Participants can choose their player character, and the inclusion of old-time celebrities as non-player characters, along with short written conversations with these celebrities, aims to create a sense of belonging for older adults. In some stages the guests may ask for a change in the shopping list, for example because of an allergy, that need to be considered by the player.

G3's design includes several features to enhance its appeal and effectiveness for older adults. Using a familiar scenario like shopping increases the ecological validity of the game. The option to select a male or female older adult character helps develop a sense of belonging, while the ability to pause and start the game easily improves the sense of autonomy. The goal of the game is straightforward, making the instructions easy to understand. The difficulty levels are aligned with the abilities of most older adults, ensuring that the game is challenging yet accessible. The original game was designed for a large touchscreen measuring 24 inches by 80 inches. GRRIT collaborated with two companies, Rebel Parachute and Beach & Lanes, to transform the game into an app for iOS and Android tablets. The game was redesigned to fit smaller screens and various tablet shapes for a free commercial version of G3. However, for this study, a computer-based version that can automatically record game metrics will be used.

3.6 Variables

The study variables are the following:

- Game performance collected through various game metrics, including total time of
 playing, the ability to complete the whole game, the ability to manage the budget, number
 of errors, the number of checking the shopping list, and the game performance accuracy.
 - Total Time of playing: This numerical variable refers to the total time that takes to complete all 6 stages in seconds with the maximum of 1800 seconds.
 - The ability to complete the game: This binary variable (1= Could complete, 0= Could not complete) refers to the participant's ability to complete all the 6 stages of the game.
 - The ability to manage the budget: This binary variable (1 = Could manage, 0 =
 Could not manage) refers to the participant's ability to keep their purchases equal to or below the budget limit provided for each level.
 - The number of errors: This numerical variable refers to the total number of mistakes made by participants, including mistaken, missed, and repeated items purchased.
 - The number of times the participant opens up the reading list: This numerical variable refers to the total number of times the participant open and check the shopping list within the 6 stages.
 - O The game accuracy: This numerical variable represents the success in the game, ranging from 0 to 100, where higher values mean higher game performance.

Demographics

 Age (In number of years): It refers to the chronological age of an individual in years at the time of data collection. This variable is considered as numerical in this study.

- Sex at birth: It refers to sex assigned at birth. Categories for this variable are male and female.
- Level of education: It refers to the highest degree or level of school completed by the participants. Categories for this variable are elementary school, high school, bachelor's degree, master's degree, and higher.
- Technology savvy: This categorical refers to the familiarity and experience of the
 participants with technology. It will be collected and measured based on the
 number of technological devices they use and the frequency of their usage.
- Living status: It refers to the participants' living condition. Categories for this
 variable are living alone, living with family, and living in an institution
- Cognitive status: It refers to the level of cognitive functioning. This variable includes two components: the MoCA score, ranging from 0 to 30, and the QuickMCI (Qmci) score, ranging from 0 to 100 for RQ2, investigating the correlation between game performance and cognitive status. Cognitive status is also defined as a binary variable, indicating whether the participant has MCI (1) or does not have MCI (0) for RQ4 that investigates the associated factors to MCI.
- State anxiety level: This numerical variable refers to the participant's anxiety levels when administering the traditional cognitive screenings and when playing the game. It is measured through the State-Trait Anxiety Inventory and ranging from 20-80. The higher scores correspond to the higher level of anxiety.
- System usability: This numerical variable refers to the quality attribute that indicate how easily users can utilize a technology. It is measured through System Usability Scale

(SUS), which ranges from 0-100 (152). Higher scores correspond to more usability of the technology.

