3.9 Data analysis

To explore the difference between game performance in PwMCI and healthy comparison group (RQ1), the Unpaired t-test or Mann-Whitney U test as appropriate (155), with an α level of 0.05, will be applied. If the mean difference is statistically significant, it indicates that G3 can classified older adults with typical cognition and older adults with MCI based on their game performance. In addition, a two-way factorial multiple analysis of covariance (MANCOVA) (155) will be performed to compare the effects of demographics as covariates on the differences between groups.

To explore the association between the game performance and traditional cognitive tests, including MoCA and Qmci (RQ2), correlational analysis (155) between the game metrics and the scores of each traditional cognitive tests, including total score sub-scores such as memory and executive functions will be conducted. If the correlation coefficient (r) is positive closer to one, it means that the concurrent validity of G3 as an MCI screening tool is good.

To investigate the diagnostic accuracy of the game-based screening (RQ3), formulas will be used as follows:

Sensitivity: Proportion of true positives correctly identified = $\frac{TP}{TP+FN}$

Specificity: Proportion of true negatives correctly identified = $\frac{TN}{TN+FP}$

Accuracy: Overall correctness of the testx = $\frac{\text{TP+TN}}{\text{Total Population}}$

Where TP: True Positives, TN: True Negatives, FN: False Negatives, FP: False Positives (155). Additionally, the interpretation of the Receiver Operating Characteristic (ROC) and Area Under the Curve (AUC) will be used for examination of diagnostic accuracy (155). The ROC curve is a graphical plot that illustrates the diagnostic ability of a binary classifier system as its discrimination threshold is varied. The curve is created by plotting the True Positive Rate (TPR) against the False Positive Rate (FPR) at various threshold settings (155).

The following steps will be used to calculate the ROC curve:

Firstly, the True Positive Rate (TPR), also known as sensitivity or recall, will be determined using the formula:

$$TPR = \frac{TP}{TP + FN}$$

Secondly, the False Positive Rate (FPR), also known as (1 - specificity), will be determined using the formula:

$$FPR = \frac{FP}{FP+TN}$$

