Finally, the ROC curve will be calculated and plotted. TPR and FPR need to be calculated for various threshold values. Then, TPR (y-axis) against FPR (x-axis) for each threshold will be plotted. The closer the ROC curve is to the upper left corner, the higher the test's accuracy, as this position represents a sensitivity of 1 and a false positive rate of 0 (specificity of 1). An ideal ROC curve has an AUC of 1.0. An AUC of 0.5 indicates no discrimination, 0.7 to 0.8 is acceptable, 0.8 to 0.9 is excellent, and above 0.9 is considered outstanding (155,156).

To investigate if the game performance is an associated factor with cognitive status controlled by demographic variables (RQ4), logistic regression analysis (157) will be used. For all variables, categories will be combined into broader categories, when possible, to improve the power of the logistic regression model (158). Chi-Square test will be used to determine if there is a significant

association between variables and cognitive status. Principal Component Analysis (PCA) will be used to reduce the number of variables in a dataset while preserving as much variability (information) as possible (159). To determines which factors to retain based on explained variance, and Eigenvalue Cut-Off of 1 will be applied. Following this, logistic regression model will be run with the included variables. The performance of the logistic regression model with be evaluated using ROC analysis and test characteristics (160).

To compare the differences between the level of anxiety while playing the game and while traditional cognitive tests in older adults with typical cognition and with MCI (RQ5), either the Paired t-test or Wilcoxon Signed-Ranks test (155) will be used as appropriate, with an α level of 0.05, to compare the anxiety level in the two conditions- while playing the games and while performing MoCA. If the mean difference is significant and lower while playing the game compared with MoCA and Qmci, it means that the G3 causes less anxiety compared to the traditional cognitive screening tools.

To explore the usability of the game-based screening (RQ6), the SUS results will be calculated and interpreted as follows:

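### Completion and budget management are each reduced to one yes/no value over six stages, which costs information in RQ1 to RQ3; stage counts would keep it at little cost

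*Protocol*

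**What the plan says.** Protocol section 3.6 lists six game metrics. Four are numerical: playing time up to 1800 seconds, errors, list checks, and accuracy from 0 to 100. Two are coded 0/1:

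- Completion "refers to the participant's ability to complete all the 6 stages of the game".
- Budget management is the "ability to keep their purchases equal to or below the budget limit provided for each level". A limit exists for each level, but nothing says how the levels combine into the single 0/1 value.

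On what is observed, section 3.5.2 says "six stages will be selected for participants to play" and "a computer-based version that can automatically record game metrics will be used". Section 3.8 adds that the stages run from easy to hard.

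On analysis, section 3.9 applies "the Unpaired t-test or Mann-Whitney U test as appropriate" for RQ1 at a level of 0.05. RQ2 correlates the game metrics with the MoCA and Qmci scores and reads a positive coefficient near one as good concurrent validity. RQ3 uses sensitivity, specificity, accuracy and a ROC curve, for which "TPR and FPR need to be calculated for various threshold values". A chi-square test is named only under RQ4. Section 3.3 sets 29 participants per group.

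**The concern.** A participant who stops in the first stage and one who stops in the last both score 0 on completion. If budget is scored the same way, a single overspend counts the same as overspending throughout. With stages ordered by difficulty, how far a person gets is a natural severity scale, and the 0/1 value keeps only its top step.

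Each of the first three research questions works better with a graded scale. RQ1 compares groups of 29, so lost information becomes lost power. RQ2 judges validity by closeness to one, which a 0/1 metric cannot normally approach. RQ3 looks for a cut-off, and a 0/1 metric offers only one. Two of the six candidate screening metrics are affected.

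**Working it through.** **Inputs from the Protocol.** Six stages (3.5.2); 29 per group and alpha 0.05 (3.3, 3.9). Sidedness is not stated; two-sided is used here.

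**Inputs assumed.** The Protocol gives no stage-level success rates and no within-person correlation. Per-stage success (typical vs MCI) was set at 0.95/0.85, 0.90/0.75, 0.85/0.70, 0.80/0.60 and 0.70/0.50. Clustering was beta-binomial with precision k, so the within-person correlation is 1/(k+1): 0.09 for k=10, 0.14 for k=6, 0.25 for k=3.

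**The plan's own figure.** The 58 in section 3.3 was not derived for these metrics. It is reproduced by a one-sided comparison of two independent correlations with q = 0.7: n = 2(1.645 + 0.842)²/0.7² + 3 = 28.2, so 29 per group. The Protocol does not state that calculation, and nothing below depends on it; 29 per group is taken as given.

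**Step 1: are the named tests valid on 0/1 data?** Take 22/29 against 14/29 successes. The t-test gives p = 0.031, Mann-Whitney 0.032, uncorrected chi-square 0.030 and Fisher's exact test 0.057. With equal groups (0.80 per stage in both), the t-test on the 0/1 value rejected in 4.3% to 4.8% of runs. So they are valid.

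**Step 2: power for RQ1.** There were 3,000 simulated trials per scenario. The 0-6 count was tested by Mann-Whitney and the all-six 0/1 value by chi-square. Cells give count vs 0/1 power in percent; a dash means that the combination is not reported here.

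| Per-stage success | k=10 | k=6 | k=3 |
|---|---|---|---|
| 0.95 / 0.85 | 77 vs 72 | 73 vs 69 | 63 vs 61 |
| 0.90 / 0.75 | 87 vs 78 | 83 vs 74 | 74 vs 69 |
| 0.85 / 0.70 | – | 72 vs 57 | – |
| 0.80 / 0.60 | 91 vs 66 | – | 78 vs 64 |
| 0.70 / 0.50 | 87 vs 45 | 81 vs 43 | 72 vs 45 |

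The largest clustered gap is 87 − 45 = 42 points and the smallest in the table is 63 − 61 = 2. With still stronger clustering (k=1.5, correlation 1/2.5 = 0.40), 0.90/0.75 gives 63 vs 60. Fully independent stages would stretch the gap to 64 points (96 vs 32 at 0.70/0.50), but independence within a person is unrealistic.

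The table treats the stages as exchangeable, which suits budget better than completion, because completed stages are nested. Under assumed models in which the 1800-second limit decides how many stages are finished, the count gave between 58 vs 57 and 87 vs 56.

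**Step 3: correlation for RQ2.** If a normal trait underlies a 0/1 metric with success share p, its correlation with that trait cannot exceed φ(z_p)/√(p(1−p)). At 50/50 this is 0.399/0.5 = 0.80; at 90/10 it is 0.58; at 95/5 it is 0.47.

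**Step 4: ROC for RQ3.** A 0/1 metric has one non-trivial operating point and AUC = (sensitivity + specificity)/2. Across the k=10, k=3 and independent-stage scenarios, AUC for count vs 0/1 ran from 0.64 vs 0.64 (least loss) to 0.76 vs 0.55 (most loss, independent stages).

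**The case against.** A reader might infer that the t-test, correlation and ROC methods do not fit 0/1 variables. The documents do not support that. Step 1 shows the group tests behave almost as chi-square does. A correlation with a binary metric is the point-biserial coefficient. Sensitivity, specificity and accuracy at the single cut are legitimate. Section 3.9 also leaves the choice of test open to suitability, although the two it names for RQ1 are not tests of proportions.

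A reader might also take it as fact that one overspend in six scores the same as six. That is explicit only for completion. For budget it is an inference, because section 3.6 gives no combining rule. The gap in the text is the missing rule.

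Third, RQ1 to RQ3 do not rest on these two metrics. Four numerical metrics suit the named methods, and neither 0/1 metric is called primary. That stands, but none of the four explicitly grades overspending or how far a participant got.

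Fourth, the size is uncertain. Section 3.5.2 says the difficulty matches most older adults, so pass rates may be high and the gain small. Differences concentrated on the last, hardest stages also shrink it: one such assumed pattern gave 83% vs 81%. This stands in full and limits how strongly the point can be put.

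Last, a yes/no result is easy to interpret in a feasibility study. That supports keeping it as a summary, not making it the only analysed form.

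**Conclusion.** The point holds as one of efficiency and definition. Two of six metrics are coded more coarsely than the play that produces them, and the budget metric cannot be scored reproducibly as written. The count had the higher power in every scenario simulated. With 29 per group and within-person clustering, the gain ran from about 1 to roughly 40 percentage points, smallest near ceiling or with strong clustering. The direction is secure; the size depends on stage-level rates and clustering that the Protocol does not give. The capped coefficient in RQ2 (under a normal latent trait) and the single operating point in RQ3 follow from the 0/1 coding itself. Nothing here makes a planned test invalid or affects the four numerical metrics. It is a cheap improvement.

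**What to change.** In section 3.6, define the analysed metrics as:

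- the number of stages completed (0-6);
- the number of levels within budget (0-6), or the proportion of attempted levels within budget, with a written rule for stages not reached.

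In section 3.9, analyse both with Mann-Whitney for RQ1, Spearman correlation for RQ2 and ROC for RQ3. Keep the yes/no versions as summaries, state how levels combine for budget, and compare them by chi-square or Fisher's exact test.

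Before data collection, confirm that the game log keeps stage-level results. Section 3.5.2 promises automatic recording but not at that level; if the log does keep them, no new data are needed.

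The cost is two definitions and a few lines of analysis text. There are two drawbacks. For non-completers the budget count partly mixes budget control with completion. Counts are also slightly less simple to read than yes/no.

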3.7 Recruitment

An email containing information about the study will be sent to partner organizations, including hospitals, memory clinics, day programs, assisted living facilities, retirement homes, and community groups. Additionally, flyers will be posted in various locations within the University of Alberta Medical Clinics, at community organizations that agree to support the study, and on social media platforms. The flyers will provide details about the research opportunity and the contact information of the researcher.

If an organization shows interest, an information session will be held to provide further details about the project and address any questions from the staff and potential participants. Older adults from these partner organizations who can provide informed consent and are interested in participating can directly contact the researcher to obtain more information or express their interest in participating. Individuals who see the flyer and contact the researcher can ask questions and receive more information through email, phone calls, or in-person or online meetings.

Interested older adults who meet the inclusion criteria will provide their contact information to the researcher to schedule an introductory session and a potential data collection session. During the introductory session, potential participants will learn about G3, its functionalities, and how to use the computer to play the game. The potential participant will be also asked to read some sentences aloud to ensure they can follow the instructions, read, and understand the content. The researcher will screen participants based on the inclusion and exclusion criteria, observing for any physical or communication difficulties that could negatively impact their engagement with

the game. Even if participants do not meet the inclusion criteria, they will still be allowed to play the game to maintain their dignity.

Those who meet the inclusion criteria and express interest in the study will sign a consent form provided by the researcher. The researcher will facilitate this process to ensure all participants clearly understand what their participation involves and the nature of the study. Participants will have the opportunity to play the Level 1 of the game to become familiar with the laptop and the game itself. Following consent, the researcher, in collaboration with the partner organization if applicable, will schedule the data collection session either on the same day or at a later date.

3.8 Data collection

Following the introductory part and the signing of the consent form by potential participants, demographic information will be gathered. Measurements for state anxiety will be administered before doing the cognitive test and before playing the game. The MoCA and Qmci for assessing cognitive status, will be administered following assessing the state anxiety. Participants will then have the opportunity to play G3 across six stages featuring three difficulty levels: easy, normal, and hard in a progressive order based on the items in the shopping list. The difficulty levels are determined by the number of items on the shopping list, allowing for a progressive challenge to their cognitive abilities within a controlled environment. After completing the game, the SUS will be administered. All measurements are expected to be conducted in a single data collection session, lasting approximately 120 minutes. If participants feel tired or need a break, accommodations will be made to ensure their comfort and well-being, including the option to take breaks or reschedule the session as needed. Assessments that will be used in the data collection are as follows:

• Montreal Cognitive Assessment (MoCA)

MoCA is one of the most common paper-based cognitive tests that has been discussed earlier in this proposal.

• Quick mild cognitive impairment (Qmci)

Qmci is one of the paper-based cognitive tests that has been discussed earlier in this proposal.

• State-Trait Anxiety Inventory (STAI)

The Spielberger STAI is a paper-based self-administered instrument comprising 40 items, designed to independently evaluate State Anxiety (S-Anxiety) and Trait Anxiety (T-Anxiety). S-Anxiety, assessed through 20 items, reflects a transient emotional condition influenced by the current situational context, wherein respondents indicate their immediate feelings. Conversely, T-Anxiety, also measured through 20 items, denotes a stable predisposition towards anxiety, with respondents reporting their general feelings (153). This STAI demonstrated robust psychometric properties. Test-retest reliability for the T-Anxiety subscale is high, indicating stability, whereas the S-Anxiety subscale is less stable, reflecting situational influences. Internal consistency is strong for both T-Anxiety and S-Anxiety (154). Concurrent validity is supported by strong correlations with other anxiety measures, and construct validity is evidenced by higher scores among psychiatric patients and during stressful situations (154). The total score ranges from 20 to 80, with scores of 20–39 indicating low anxiety, 40–59 indicating moderate anxiety, and 60–80 indicating high anxiety (153). In this study, the state anxiety score will be used to compare the level of anxiety experienced during the administration of traditional cognitive screening tests (i.e. MoCA and Qmci) and while playing the G3 game.

• System Usability Scale (SUS)

SUS is a paper-based, simple, subjective, 10-item scale that provides a general view of usability.

Each item on this Likert scale presents a statement, and respondents indicate their degree of

agreement or disagreement on a 5-point scale. The SUS is typically used after respondents have had an opportunity to use the system being evaluated, but before any discussion occurs. Respondents should provide their instant responses to each item without overthinking. The final score ranges from 0 to 100 (Ref).

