1.3 Research questions

The present study aims to respond the following research questions (RQ).

- 1. Is there any difference between the game performance of older adults with typical cognition and individuals with MCI?
- 2. What is the concurrent validity of the game-based screening for MCI detection?
 - 2.1 Is there any relationship between game performance and total score of traditional cognitive tests (MoCA score and Quick MCI (Qmci)) in older adults with typical cognitive and older adults with MCI?
 - 2.2 Is there any relationship between the sub-MoCA scores and sub-Qmci scores and the game metrics in older adults with typical cognitive and older adults with MCI?

- 3. What is the diagnostic accuracy of the game-based screening assessed by sensitivity, specificity, accuracy, and the Area Under Curve (AUC) of the game-based screening for MCI detection?
- 4. Is game performance an associated factor with cognitive status controlled by demographic variables?
- 5. Is there any difference between the level of state anxiety while playing the G3 game and while administering traditional cognitive tests in older adults with typical cognition and individuals with MCI?
- 6. What is the usability of the G3 as a game-based screening?

2. Literature review

This chapter will address several key areas essential for understanding the use of SCGs in cognitive screening for MCI. It will begin with an overview of cognitive functions and their domains, followed by a discussion of MCI, its prevalence, and associated brain changes. The review will then examine cognitive changes with aging and MCI, traditional cognitive tests used for MCI diagnosis, and their limitations. It will explore digital technologies for MCI screening, focusing on the potential of SCGs. Finally, the chapter will highlight research gaps and propose directions future studies, emphasizing the investigation of the G3, a SCG designed for older adults, for MCI detection.

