
2.2.6 Advantages and disadvantages of cognitive tests

The cognitive tests can distinguish cognitive impairment from normal aging and specify and quantify the area of impairment (19). They are widely recognized in clinical practice for their proven psychometric properties (118). Moreover, they are often administered in paper-and-pencil format, which is straightforward and familiar for older adults. Despite the merits, cognitive tests have some limitations. Scoring can be subjective, leading to potential human errors and affecting test accuracy (20). These tests often fail to represent the complexity of real-life tasks (21). Moreover, the need for trained clinicians to administer the test restricts access, making continuous monitoring of cognitive changes difficult and costly (22,23). Traditional cognitive tests could induce state anxiety, an "in-the-moment" measure of anxiety as described subjectively by an individual, in older adults (24,119), potentially leading to test avoidance or negatively affecting their cognitive performance (25). The tests could be perceived as a threat (120), particularly among older adults who may have concerns about their cognitive health and the implications of receiving a low score. Such concerns could include potential changes in their living arrangements or decreased autonomy. This anxiety might divert attention toward the

threat, therefore reducing cognitive performance during the tests (120) and leading to potential misinterpretation of results and implications for MCI screening.

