SCGs also offer the potential advantages of adaptability and customization for screening different cognitive domains (127), which can improve user motivation and acceptance (128). The difficulty and features of SCGs could be adjusted dynamically based on the player's performance, needs, and preferences (128,129). This contrasts with traditional tests that often offer inflexible formats. However, more research is needed to explore the full potential of this adaptability and customization (129).

SCGs can also incorporate ADL and iADL within the game scenarios (27), offering a more realistic measurement of cognitive abilities and reflecting how impairments might affect everyday tasks (130,131). The home-based and self-administered aspects combined with ADL and iADL simulation, enhances the ecological validity of SCGs compared to traditional tests administered in clinical settings, which often lack real-life components (132).

Moreover, SCGs provide an engaging and enjoyable experience, potentially reducing the anxiety often induced by traditional tests in older adults (24). Research suggested that using video games could cut the influence of the white coat effect, the anxiety resulted from being assessed by a health care professional (133) and the overwhelming feeling associated with traditional screening methods (118). The stress-relieving benefits of video games have been also reported by older adults who play them (32). However, no research has been done to examine the different levels

of anxiety among older adults with and without cognitive impairments while doing the traditional tests and playing an SCG.

Despite the advantages, SCGs present several limitations. A primary concern is the reluctance of many older adults to engage with new technological devices (134) and potential of experiencing technology anxiety among older adults, making the application of SCGs challenging (135). In contrast, older adults might be more familiar with the process of performing traditional tests. Additionally, SCGs have not been integrated into standard clinical practice (135), partly due to the lack of a set of standardized guidelines and normative data that are necessary for clinical interpretation (133). However, traditional tests have well-established psychometric properties and are commonly used in clinical practice (118).

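### Research question 5 asks about anxiety during the tests and during play, but the state scale is given before each task with the tests first, so the planned causal reading is unsupported

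*Protocol*

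**What the plan says.** Four places in the protocol set the target as anxiety during the two tasks.

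- Section 1.3, research question 5: "Is there any difference between the level of state anxiety while playing the G3 game and while administering traditional cognitive tests".
- Section 3.6 defines the variable as the participant's "anxiety levels when administering the traditional cognitive screenings and when playing the game".
- Section 3.8, under the STAI, says the state score will be used to "compare the level of anxiety experienced during the administration of traditional cognitive screening tests" with the anxiety felt during play.
- Section 3.9 compares the condition of playing with the condition of performing the MoCA, by a paired t-test or Wilcoxon signed-ranks test at alpha 0.05. It reads a significantly lower game score as showing that G3 causes less anxiety than the traditional tools.

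Only the opening paragraph of section 3.8 schedules the scale: "Measurements for state anxiety will be administered before doing the cognitive test and before playing the game". The MoCA and Qmci follow the anxiety assessment, G3 comes next, and the SUS follows the game.

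On the instrument, section 2.2.6 calls state anxiety an in-the-moment "measure of anxiety as described subjectively by an individual", and section 3.8 describes the state items as ones "wherein respondents indicate their immediate feelings".

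**The concern.** A scale that asks how the respondent feels now, completed before a task, measures anticipation of that task. It cannot record what the person felt during play that had not yet begun. The protocol nevertheless labels, analyses and interprets the scores as anxiety during the tasks.

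The fixed order adds a second problem. The game score is also the later score, so relief, habituation, fatigue or residual test anxiety would all enter the paired difference.

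If the plan is followed as written, a significant result will be reported as a causal finding about two tasks, from scores taken before them in one order. Section 2.3.4 presents the comparison of anxiety "while doing the traditional tests and playing an SCG" as a gap in the literature. That gap would be reported as filled when it is still open.

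**Working it through.** The protocol gives no power calculation, expected difference or SD for research question 5, so there is no figure to reproduce. The check compares the passages and then asks how little is needed to meet the rule in 3.9.

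**1. Timing against target**

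| Place | Moment referred to |
|---|---|
| 1.3, research question 5 | during the tests, during play |
| 3.6, state anxiety | during the tests, during play |
| 3.8, STAI paragraph | during the tests, during play |
| 3.9, analysis | during the MoCA, during play |
| 3.8, schedule | before the tests, before play |

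Readings scheduled: 2. Readings during or after the game stages: 0. Maximum game time (3.6): 1800 s / 60 = 30 min.

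**2. Order**

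Section 3.8 describes one sequence: state scale, MoCA and Qmci, then G3. The paired test needs two scores, so the before-game reading naturally falls between the tests and the game. Section 2.2.5 gives the MoCA 10–15 min and the Qmci 3–5 min, so that reading comes after a nominal 10 + 3 = 13 to 15 + 5 = 20 min of the comparator task, not counting any breaks or rescheduling.

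**3. Prior exposure**

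Section 3.7 offers play of Level 1 beforehand and describes no matching practice for the tests. That could lower pre-game anxiety. Section 2.3.4 points the other way: "older adults might be more familiar with the process of performing traditional tests", and it adds that technology may itself provoke anxiety. The net direction is unknown.

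**4. What meets the rule in 3.9**

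The smallest observed mean difference that is significant in a paired t-test, taken as two-sided (the protocol does not state sidedness), in SDs of the paired difference, is t(0.975, n−1) / √n.

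- n = 58: 2.0025 / 7.6158 = 0.263
- n = 29 (one group): 2.0484 / 5.3852 = 0.380

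The SD of the paired difference is not given. For assumed values at n = 58, on the 20–80 scale:

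| Assumed SD | Threshold, points |
|---|---|
| 5 | 1.31 |
| 10 | 2.63 |
| 15 | 3.94 |

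A mean reduction of this size triggers the causal sentence whatever produced it. Because the size and sign of any order or familiarity effect are unknown, no error rate is claimed.

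**The case against.** The contradiction in timing is hard to dispute, but several points can be made in the protocol's favour.

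- **The thresholds do not measure the flaw.** The values 0.263 and 0.380 belong to any paired t-test of that size, and would be the same with ideal timing and a balanced order. They do not apply to the Wilcoxon test that 3.9 also allows, and the SDs are assumed. This stands. The figures only show how small a shift meets the rule; the substantive count is that no reading falls during or after play.
- **The place of the second reading is inferred.** Section 3.8 does not expressly put a form between the Qmci and G3. That is true, but it is the natural reading and the paired test requires it. If both readings came before both tasks, neither would measure anxiety during play and the contradiction would remain.
- **Order and familiarity are secondary.** Lack of counterbalancing in a feasibility study, on a non-primary question, is largely a matter of preference. Section 3.11 already mentions mood, time of day and location as examples of transient influences. This stands as to weight, but task order and prior game exposure are not named, and causal wording needs more than this design provides.
- **Pre-task anxiety is worth measuring.** Section 2.2.6 links test anxiety to avoidance and describes tests as a perceived threat, which is partly anticipation. This stands: the scores are mislabelled, not worthless.

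Leaving the matter to a statistical analysis plan would not resolve it. Section 3.8 fixes the timing, 3.9 fixes the conclusion, and an analysis plan cannot supply readings that were never taken.

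**Conclusion.** The concern holds. The schedule in 3.8 conflicts with research question 5, the variable definition, the STAI paragraph and the analysis, and the causal reading in 3.9 does not follow from the scores that would be collected. This should be fixed.

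The conclusion rests on the protocol's own wording and on taking the before-game form to follow the tests. It needs no assumed SD and no assumed order effect. The direction of bias is unknown: the plan could suggest a benefit that is not there or hide one that is.

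The reach is limited. Section 3.3 names diagnostic accuracy and validity testing as the primary objectives, and no other analysis uses the anxiety score.

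**What to change.** Either of two changes would do.

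**(a) Wording only, and sufficient.** In 1.3 (research question 5), 3.6, the STAI paragraph of 3.8, and 3.9, refer to pre-task (anticipatory) anxiety. Replace the causal sentence in 3.9 with, for example: *A lower score before the game than before the MoCA and Qmci is a difference in pre-task anxiety with the tests given first; it does not show that G3 causes less anxiety.* In the same edit, reconcile 3.9 with itself: it compares play with the MoCA alone but interprets against the MoCA and Qmci together. In 3.11, add task order and prior game exposure, and say that anxiety during the tasks remains unstudied. Data collection does not change.

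**(b) If anxiety during the tasks is to remain the question.** In 3.8, keep the first form as a baseline, replace the before-game form with one given immediately after the cognitive tests, and add one immediately after the game. Both post-task forms should ask how the participant felt during the task just completed. The causal wording should still go, and the fixed order should be stated as a limitation. The cost is three 20-item forms instead of two (60 items instead of 40) in a session of about 120 minutes. The reading also becomes retrospective, which departs from the immediate-feelings instruction that 3.8 describes.

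Neither change alters task order or the data for research questions 1 to 4. Counterbalancing is optional. A MoCA score of 18 or higher is an entry criterion, which makes tests-first convenient, although 3.7 lets people who do not qualify play anyway, so that order is not strictly forced.
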